2.2 Part B Objectives

2.2.1 Part B1 Objectives

Primary Objective:

- To assess the efficacy of treatment with seviprotoimut-L compared to placebo with respect to recurrence-free survival

Secondary Objectives:

- To assess the efficacy of treatment with seviprotoimut-L compared to placebo with respect to overall survival
- To verify the safety and tolerability of seviprotoimut-L at the dose selected for Part B.
- To assess a potential correlation between biomarker shifts/baseline prognostic markers and clinical outcome

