6.9.3 Sensitivity Analyses of Efficacy Endpoints

6.9.3.1 Sensitivity Analyses of Overall Survival (OS)

The following sensitivity analyses for OS will be performed:

- The primary OS analysis will be performed using the ATAS.
- Deaths that occur after the cutoff will not be censored.
- Clinical site homogeneity will be assessed by testing the arm by site or site class interaction. This open-ended exploration will assess homogeneity across sites using the following clumping of sites: Clinical sites with patients fewer than K patients in either arm will be pooled into a single pseudo clinical site. K will be varied in the range of 2 to 8. Classes of clinical sites will be analyzed according to characteristics such as region, type of facility, or homogeneity of medical practice for treating melanoma.
- The proportional hazard regression (PHR) will be re-run without the strata statement and with the treatment arm by stratum interaction term added to the model statement in order to assess the interaction between the treatment arms and the disease states at randomization.
- Effect modifier analyses will be performed for base attributes and particularly putatively prognostic factors, including those explored previously in the literature as well as those hypothesized to be predictive in the context of this study. These are listed subsequently. Effect modification will be assessed one factor at a time in stratified PHR models. Each factor will be analyzed as either a natural dichotomy, a dichotomized ordered categorical with cutpoint chosen based on biologic considerations, or a continuous variable dichotomized at the overall median, and possibly tertiles, quartiles or quintiles. A separate hazard ratio estimate for arm and its 95% confidence interval will be computed for each level of the categorical attribute

using contrast statements in SAS PROC PHREG. Kaplan-Meier estimates of combinations of arm by factor will be plotted on.

- Proportional hazard regression models with multiple added prognostic covariates will be estimated. The covariates to be added will include those explored previously in the literature as well as those hypothesized to be predictive in the context of this study. Interactions will also be explored for contribution to the model.

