6.9.3.2 Sensitivity Analyses of Recurrence-free Survival (RFS)

The following sensitivity analyses for RFS will be performed:

- The same sensitivity analyses specified for as sensitivity analyses of survival will be done for RFS.
- Sensitivity analyses of alternative coding of the date of recurrences and censoring will be performed. These analyses will follow the suggestions in the FDA Guidance for Industry Clinical Trial Endpoints for the Approval of Cancer Drugs and Biologics, May 2007 ([Appendix 3](#)).

All secondary efficacy analyses and sensitivity analyses will be presented by randomized treatment, based on the ITT analysis set, unless otherwise specified.

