6.9.4 Base Attributes to be Assessed

As specified under sensitivity analyses for RFS and Survival analyses the relationship between outcomes and base attributes are planned to be conducted. These base attributes include but are not limited to:

- Stage of disease (Stage IIB v Stage III)
- Sex (F vs. M), age (< 60 vs. \geq 60)
- ECOG Performance Status (0 vs. 1)
- Presence of ulceration (present vs. absent)
- Site (extremity vs. trunk)
- Lymph node status (sentinel LN only positive vs. other)
- Antibody response (positive vs. negative)
- Elispot response (positive vs. negative)
- BRAF tumor mutation status

- Source of the patient (clinical site or various site classes)

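### The effect-modifier analysis in SAP 6.9.3.1 handles continuous factors only as categories; a continuous-scale arm-by-factor interaction should be prespecified alongside fixed display cuts

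*SAP*

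**What the plan says.** SAP 6.9.3.1 lists sensitivity analyses for OS. One bullet covers effect modification: "Effect modification will be assessed one factor at a time in stratified PHR models". It gives three forms for a factor: a natural dichotomy, an ordered category cut in two, or "a continuous variable dichotomized at the overall median, and possibly tertiles, quartiles or quintiles". All three are categorical. The stated output is also by category: "A separate hazard ratio estimate for arm and its 95% confidence interval will be computed for each level of the categorical attribute", with Kaplan-Meier curves by arm and factor. The bullet names no interaction test, significance level or power.

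SAP 6.9.3.2 carries this to the other primary endpoint: "The same sensitivity analyses specified for as sensitivity analyses of survival will be done for RFS".

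SAP 6.9.4 lists the attributes ("Sex (F vs. M), age (< 60" and so on). Age, with its cut at 60, is the only clearly continuous one; SAP 3.8 gives the same cut. Both sections leave the list open to additions.

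Two other places set no categorisation. The next bullet of 6.9.3.1 says "Proportional hazard regression models with multiple added prognostic covariates will be estimated" and "Interactions will also be explored for contribution to the model", without stating a scale. SAP 6.10.2 relates serial biomarkers and laboratory values to outcome through time-dependent covariates. Addendum #1 leaves all of this text unchanged.

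**The concern.** If the benefit of the vaccine changes gradually with age or with a baseline marker, cutting the factor in two discards the ordering within each half. The analysis meant to show who benefits then has less chance of showing it than the same Cox model with the factor left on its own scale.

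The wording also allows four groupings (halves, thirds, quarters, fifths) with no rule for choosing among them. For a continuous factor added to the list, the grouping could be chosen after the results are seen.

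This is of practical interest here. Protocol 9.3.2 says that tests for possible subject selection will be investigated, and Protocol 3.5.2 and 3.5.3 refer to the SAP for how the endpoints relate to prognostic factors.

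**Working it through.** **Reproducing the plan's own figure.** The documents give no power for any effect-modifier analysis, so the nearest stated figure is the Part B1 RFS power. Inputs from SAP 5.2.1 and 2.2: 325 patients in 1.5 years, 2:1 allocation, 126 events, one-sided 0.10, stage mix 30.9/30.4/38.7%, control medians 4.5, 3.5 and 1.7 years, and HR 1 for 1 month falling linearly over 3 months to 0.625. A 1-year accrual ramp was assumed. Simulated power is 81 to 82%, against the stated 80.5%. The event counts and allocation are therefore a sound base for what follows.

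**Assumptions not in the documents.** Two-sided 0.05, a normally distributed factor, and a log hazard ratio that is linear in the factor. The interaction size θ (ratio of hazard ratios per SD) is varied.

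**Continuous scale.** With D events and a share p on vaccine, the interaction Z statistic has mean √(D·p(1−p))·ln θ.

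- B1: √(126 × 2/3 × 1/3) = 5.29.
- B2 RFS: √(310 × 1/2 × 1/2) = 8.80.

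Power of 80% needs a mean of 1.960 + 0.842 = 2.802, and 90% needs 1.960 + 1.282 = 3.242. The θ required is:

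- B1: exp(2.802/5.29) = 1.70 and exp(3.242/5.29) = 1.85.
- B2: exp(2.802/8.80) = 1.37 and exp(3.242/8.80) = 1.45.

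**After a split.** A cut with share q on one side, at normal quantile c, keeps the fraction φ(c)²/(q(1−q)) of the information. At the median this is 2/π = 0.637, and the mean of Z shrinks by √0.637 = 0.798.

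| Cut | Information kept | From 80% | From 90% |
|---|---|---|---|
| Median | 0.637 | 60.8% | 73.4% |
| 35/65 | 0.603 | 58.5% | 71.1% |
| 25/75 | 0.539 | 53.8% | 66.2% |

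For age cut at 60, the documents give no age distribution. Assuming a mean of 52 to 63 and an SD of 12 to 15, the loss from 80% is 19 to 26 points.

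**Simulation check.** Stage-stratified Cox models with arm, factor and their product, 600 replicates per setting (Monte Carlo SE about 2 points), continuous versus median split:

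- B1: 79.7% to 57.7%, and 91.8% to 70.8%.
- B2: 77.5% to 57.5%, and 86.7% to 66.2%.

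**How far the loss depends on the truth.** From the formula, for a median split:

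| Events | θ per SD | Continuous | Median split | Loss (points) |
|---|---|---|---|---|
| 126 | 1.2 | 16.0% | 11.7% | 4.3 |
| 126 | 1.3 | 28.4% | 19.7% | 8.7 |
| 126 | 1.6 | 70.1% | 51.0% | 19.1 |
| 310 | 1.2 | 36.1% | 24.8% | 11.3 |
| 310 | 1.35 | 75.2% | 55.9% | 19.4 |
| 310 | 1.6 | 98.5% | 91.0% | 7.5 |

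A uniform factor split at its median loses 10 to 12 points, and tertiles scored as a trend lose 8 to 10. If the true modifier is a threshold at the median, the split wins: 82% against 60% in B1, and 78% against 58% in B2.

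**Open choice of grouping.** Under no interaction, with each of the four groupings tested at 0.05 and the most favourable one reported, 400,000 simulated draws with equal information per group give about 13% false positives per factor. This is a worst case, because the SAP does not say that each grouping would be tested.

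**The case against.** The strongest reply is that the bullet specifies no test. It yields hazard ratios and curves by level, which need categories, so a loss of power is measured against a test the SAP never proposed. The analyses are headed sensitivity or exploratory, age is the only continuous factor named, and its cut is fixed. All of that is correct. It limits the importance of the point but does not supply the missing continuous analysis.

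A reader might infer that the SAP examines prognostic markers only after splitting them. The documents do not support that. The multivariable bullet and SAP 6.10.2 impose no categories. The secondary objective, "To assess a potential correlation between biomarker shifts/baseline prognostic markers and clinical outcome", concerns correlation with outcome rather than modification of the treatment effect, and Protocol 9.3.2 has the banked samples analysed separately. Equally, neither of those SAP passages commits to a continuous arm-by-factor interaction, so they do not close the gap.

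A reader might also take a loss of about 20 points as a fixed property of this plan. It is not. It needs a linear interaction, a roughly normal factor and a continuous test already near 80 to 90% power. In B1 that means an interaction of about 1.70 to 1.85 per SD, which is large. With modest interactions in B1, power is low on either scale.

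**Conclusion.** The point holds for the dedicated effect-modifier analysis of OS and RFS: continuous factors enter as categories only, and no continuous-scale interaction is prespecified. Given a normal factor, a linear log-HR interaction and two-sided 0.05, a median split costs about 19 points from 80% power and about 17 from 90%. The cost rises for off-centre cuts, falls for modest or very strong interactions, and reverses for a threshold at the cut. The room for selective reporting applies to continuous factors added to the open list, not to age. This is an inexpensive improvement to an exploratory analysis. The primary tests, error rates and event counts are unaffected.

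**What to change.** In SAP 6.9.3.1 and 6.9.4, and so for RFS under 6.9.3.2:

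- For age and any continuous baseline factor added later, name the arm-by-factor interaction on the continuous scale, in the stratified Cox model with the factor's main effect, as the assessment of effect modification. Use the log scale where the factor is skewed.
- Add a restricted cubic spline as a check on linearity.
- Report the hazard ratio across the range of the factor with its 95% band.
- Keep one fixed cut per factor (60 for age, otherwise the overall median) for the level-specific hazard ratios and Kaplan-Meier plots, where a threshold pattern would still be visible.
- Remove the optional tertiles, quartiles and quintiles.

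The cost is SAP wording, a few lines of PHREG code and one extra figure per continuous factor. No new data are needed. The downside is a linearity assumption, which the spline checks.

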6.9.3.2 Sensitivity Analyses of Recurrence-free Survival (RFS)

The following sensitivity analyses for RFS will be performed:

- The same sensitivity analyses specified for as sensitivity analyses of survival will be done for RFS.
- Sensitivity analyses of alternative coding of the date of recurrences and censoring will be performed. These analyses will follow the suggestions in the FDA Guidance for Industry Clinical Trial Endpoints for the Approval of Cancer Drugs and Biologics, May 2007 ([Appendix 3](#)).

All secondary efficacy analyses and sensitivity analyses will be presented by randomized treatment, based on the ITT analysis set, unless otherwise specified.

6.9.4 Base Attributes to be Assessed

As specified under sensitivity analyses for RFS and Survival analyses the relationship between outcomes and base attributes are planned to be conducted. These base attributes include but are not limited to:

- Stage of disease (Stage IIB v Stage III)
- Sex (F vs. M), age (< 60 vs. \geq 60)
- ECOG Performance Status (0 vs. 1)
- Presence of ulceration (present vs. absent)
- Site (extremity vs. trunk)
- Lymph node status (sentinel LN only positive vs. other)
- Antibody response (positive vs. negative)
- Elispot response (positive vs. negative)
- BRAF tumor mutation status

- Source of the patient (clinical site or various site classes)

6.10 Exploratory Analyses

6.10.1 Time-to-Event Endpoints

Additional exploratory time-to-event endpoints including time to locoregional recurrence and time to distant recurrence will be analyzed as described for RFS, including the sensitivity analyses. These analyses will be interpreted using two-sided 0.05 P values.

6.10.2 Exploratory Analyses of Other Time-Dependent Outcomes

Other time-dependent outcomes include serially assessed biomarker status, laboratory assessments, and the use of other anti-cancer interventions. These will be analyzed longitudinally using MMRM methods or as time-to-event as appropriate. In addition, the relationship between these other time-dependent outcomes and the primary outcomes will be analyzed using proportional hazard regression with time-dependent covariates.

6.11 Safety Endpoints

6.11.1 Adverse Events (AEs)

Adverse events will be coded using the MedDRA Version 14.1. Coding includes system organ class (SOC) and preferred term (PT). All verbatim descriptions and coded terms will be listed for all AEs. All adverse event tables will be presented by treatment received, based on the Safety population. AEs will be graded according to the National Cancer Institute Common Terminology Criteria for Adverse Events Version 4 (NCI-CTCAE v4) [NCI, 2009] as defined below.

| Grade | Degree of Severity |
|-------|--|
| 1 | Mild, with no or mild symptoms; not interventions required |
| 2 | Moderate; minimal intervention indicated; some limitation of activities |
| 3 | Severe but not life-threatening; hospitalization required; limitation of patient's ability to care for him/herself |
| 4 | Life-threatening; urgent intervention required |
| 5 | Death related to adverse event |

A summary of adverse events, including any AEs of special interest, will be presented for Part A, open-label extension of Part A, and Part B. A summary of AEs by PT and maximum CTCAE grade will also be presented for Parts A and B.

Treatment-emergent AEs (TEAEs)

The following AEs will be defined as TEAEs:

- AEs occurring between study drug administration and 30 days following the last dose of study drug;

- AEs started prior to study drug administration but worsened in severity following study drug administration;
- AEs with partial onset dates if the stop date is after the first study drug administration and the dates do not definitively place the AE before the start date of study drug;
- AEs with completely missing onset dates.

All AEs will be listed by patient and AE line number.

The frequency and percentage of subjects with at least one TEAE will be summarized by SOC and PT. At each summary level, a subject will be counted only once if he/she experiences one or more TEAE. The percentage of subjects having had at least one TEAE at each level will be calculated.

Tabular summaries for Part A, open-label extension of Part A, and Part B will include all TEAEs, TEAEs related to study drug, TEAEs by severity grade, serious TEAEs, serious TEAEs related to study drug and TEAEs and related TEAEs leading to permanent discontinuation of study drug. All deaths will be presented in a listing that includes the AE leading to death, demographic data, details of study treatment, and relationship to the study drug of the AE leading to death.

In instances where a subject may have multiple AEs with differing levels of severity grade or relatedness, the most severe grade or most related event, respectively, will be reported for the severity grade and relatedness tables. For the purpose of analysis, AEs with a relatedness of Probable, Possible or missing relatedness will be considered related; AEs with a relatedness of Unlikely will be considered not related. AEs with missing severity will be presented as severe in the tables but will have severity grade listed as missing.

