3 TRIAL DESIGN

3.1 Study Design Overview

The study is composed of 2 parts, Parts A and B. Part A is an evaluation of immunological activity and safety. Part B, which is also composed of two parts, Parts B1 and B2, enables a clinical efficacy evaluation.

Part A is designed to evaluate the safety and biological activity of 40 µg and 100 µg of seviprotimut-L compared to placebo, and to select a dose for Part B of the study based on immunological biomarker response (with no access to clinical outcome data). This evaluation is scheduled to take place after the first 99 randomized subjects with immune response data have reached Week 10 (5 doses of study treatment received). Enrollment into Part A will continue until completion of the Part A analysis. Missing or mishandled samples may result in not all dosed subjects being evaluable for the formal Part A analysis.

At the completion of Part A analysis, subjects receiving 40 or 100 µg seviprotimut-L will continue with the dose to which they were initially randomized in a masked manner (i.e., the subject and investigator will know the subject was receiving one of the two dose levels of seviprotimut-L, not placebo).

Subjects receiving placebo in Part A will be unmasked and removed from the study. Part A placebo subjects may be given the option of receiving treatment with seviprotimut-L (Part B dose) under open-label extension protocol 103A-301OL (Appendix C) if an investigator feels this is in the subject's best interest and the program is approved by regulatory authorities. Regardless of whether subjects receive treatment with seviprotimut-L, placebo subjects from Part A will be monitored for recurrence and vital status (survival) at least every 6 months by contacting the subjects (via telephone or at the time of routine, non-study related, office visit) until the study is terminated/completed, the subject is lost to follow-up, or the subject specifically requests to be withdrawn from vital status follow-up.

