7.2.3 Schedule and Duration of Treatment

Each subject will be treated with seviprotrumut-L or placebo until one of the following occurs: development of recurrent disease that does not meet the criteria for continued dosing (see Section 7.2.4), death, subject withdrawal or early termination, or study termination.

Doses will be administered according to the following schedule: the initial dose then every 2 weeks x 4, then monthly x 4, and then every 3 months through Month 24 (i.e., at the following time points: W0, W2, W4, W6, W8, M3, M4, M5, M6, M9, M12, M15, M18, M21, and M24).

The outcome of the Part A evaluation will not change the dose level or regimen for subjects enrolled in Part A, except for placebo subjects. Subjects receiving 40 or 100 µg seviprotilimut-L will continue with the dose to which they were initially randomized (i.e., Part A subjects will not cross into Part B). Subjects receiving placebo in Part A will be removed from the study and may be given the option of receiving treatment with seviprotilimut-L (Part B dose) under open-label extension protocol 103A-301OL (Appendix C) if an investigator feels this is in the subject's best interest and the program is approved by regulatory authorities. Regardless of whether subjects receive treatment with seviprotilimut-L, placebo subjects from Part A will be monitored for vital status (survival) at least every 6 months through telephone (or in-person) contact until the study is terminated/completed, the subject is lost to follow-up, or the subject specifically requests to be withdrawn from vital status follow-up.

Safety information from all subjects will be included in the final analysis, but only efficacy data from Part B subjects will be included in the clinical efficacy analysis for the study.

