5.0 STATISTICAL CONSIDERATIONS

5.1 Part A

The size of Part A (33 patients per arm) was computed based on having no greater than a one-sided 20% likelihood of a false positive conclusion for the immune response statistical criterion. See the subsequent section [6.8.1 “Part A Immunological Statistical Success”](#) for the statistical operating characteristics of the Part A statistical analysis.

Recruitment will continue in Part A until the analysis of Week 10 data has been completed on the first 99 randomized subjects. This will result in an “over enrollment” for Part A to avoid a discontinuation of recruitment and ensure a complete data set for Part A evaluation.

Patients assigned to the Placebo arm during Part A accrual will be offered the option of receiving 40 µg seviprotimut-L selected from Part A under an Open-Label Extension protocol. Patients assigned to the Part A active arms will remain on the dose assigned and be followed until the end of the study. All Part A patients will be separately tabulated and used in the assessment of safety. They may also be used in exploratory efficacy analyses, but will not be part of the primary or secondary Part B evaluations.

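### The final Part A adverse-event tables set crude percentages for active arms dosed to Month 24 beside a placebo arm whose window closes early by design

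*SAP*

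**What the plan says.** SAP 6.11.1 counts each subject once per summary level and reports a percentage: "The percentage of subjects having had at least one TEAE at each level will be calculated". The window covers "AEs occurring between study drug administration and 30 days following the last dose of study drug", so its length depends on how long each subject was dosed. The tables are produced separately by part: "Tabular summaries for Part A, open-label extension of Part A, and Part B will include all TEAEs".

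Protocol 3.1 says what happens when the Part A analysis is complete: "Subjects receiving placebo in Part A will be unmasked and removed from the study". From then on these subjects are contacted about recurrence and survival. Protocol 10.7.1 closes adverse-event reporting 30 days after study drug ends. Events in placebo subjects who enter the open-label extension go to that extension's own table. Subjects on 40 or 100 µg "will continue with the dose to which they were initially randomized" (Protocol 7.2.3), on a schedule that is monthly up to Month 6 "and then every 3 months through Month 24".

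The cumulative data are to be used. Protocol 7.2.3 states that "Safety information from all subjects will be included in the final analysis", and SAP 5.1 that "All Part A patients will be separately tabulated and used in the assessment of safety".

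Protocol 3.5.1 limits the Part A evaluation, safety included, to data through Week 10. In the SAP that limit stands under the primary endpoints (3.4.1). It is absent from the safety endpoints (3.4.2) and from 6.11.1. SAP 6.7 tabulates injections given and expected by group and puts exposure in listings. Neither serves as a denominator for adverse events.

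**The concern.** A percentage with at least one event rises with time at risk. If one arm is observed for less time by design, its percentage is lower even when the underlying rates are identical. In the final Part A tables the shortened arm is placebo, so the distortion runs against both doses.

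A second problem points the same way. After the Part A analysis, continuing subjects and their investigators know that the injections are vaccine and only the dose level stays masked (Protocol 3.1). Later events are therefore reported without placebo blinding, and no concurrent control remains.

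At stake is the long-term safety description of Part A. It is the trial's only randomised, placebo-controlled information on 100 µg and adds to the record on 40 µg. A reader of the final tables could take an artefact of follow-up for toxicity.

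**Working it through.** The documents give no figure for this comparison, so there is nothing to reproduce. The check asks how far crude percentages separate when the true hazards are equal.

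**Inputs from the documents**
- 15 scheduled doses from Week 0 to Month 24, nine of them by Month 6 (Protocol 7.2.3).
- Recurrence normally stops dosing. Stage mix 30.9 / 30.4 / 38.7% with rates λ = 0.154 / 0.198 / 0.409 per year (SAP 5.2.1). These agree with ln 2 / median: 0.154, 0.198 and 0.408.
- A 30-day tail after the last dose, taken as 1/12 year.

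**Assumptions**
- The same constant hazard a of a first event in every arm, 0.1 to 0.5 per year.
- No vaccine effect on recurrence.
- Placebo removed after 6 to 18 months of dosing. The documents do not give this time.

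**Formula.** For dosing planned to time T (years),

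P(T) = 1 − e^(−a/12) × Σ w [ λ/(λ+a) × (1 − e^(−(λ+a)T)) + e^(−(λ+a)T) ],

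summed over the three stage groups with weights w.

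**Worked example, a = 0.25**
- Active, T = 2: bracket values 0.657, 0.670, 0.722; weighted sum 0.686; times e^(−0.0208) = 0.979 gives 0.672. P = 32.8%.
- Placebo, T = 1: bracket values 0.794, 0.798, 0.817; weighted sum 0.804; times 0.979 gives 0.788. P = 21.2%.
- Ratio 32.8 / 21.2 = 1.55, with no true difference.

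**Range**

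| a per year | Active | Placebo out at 6 mo | at 12 mo | at 18 mo | Ratios |
|---|---|---|---|---|---|
| 0.10 | 15.0% | 5.4% | 9.2% | 12.3% | 2.80, 1.64, 1.22 |
| 0.25 | 32.8% | 12.9% | 21.2% | 27.7% | 2.55, 1.55, 1.18 |
| 0.50 | 53.4% | 24.0% | 37.6% | 47.0% | 2.23, 1.42, 1.14 |

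Mean time at risk is 19.8 months on active, against 6.6 months (removal at Month 6) or 11.6 months (Month 12) on placebo.

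**Events tied to doses.** At 2% risk per dose and ignoring recurrence, 15 doses give 1 − 0.98^15 = 26.1% and nine doses (removal just after Month 6) give 1 − 0.98^9 = 16.6%, a ratio of 1.6. The direction is the same and the size smaller.

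**Part B, for contrast.** Both arms have the same 24-month schedule. If the design hazard ratio of 0.625 with the SAP's delay holds, mean time to recurrence or Month 24 is 1.68 years on vaccine and 1.56 on placebo. The crude ratio is then about 1.06 to 1.07 over dosing. An event seen in 20% on placebo moves by 1.3 points, and one seen in 40% by 2.3 points. Without efficacy the shift is zero.

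**After the fix.** With a common cut at 12 months both arms are expected to show 21.2%. Expected time to first event or end of window is P/a, so first events per 100 subject-years are 100 × 0.328/1.312 = 25 on active and 100 × 0.212/0.849 = 25 on placebo, a ratio of 1.00.

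**The case against.** The strongest reply is that the safety evaluation that mattered was balanced. Protocol 3.5.1 cuts it at Week 10, when every arm has the same five scheduled doses, and dose selection is complete. That stands. A reader might infer that the choice of 40 µg was distorted, and the documents do not support this.

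A reader might also infer that the Part B1 safety comparison, part of the justification for Part B2, is materially biased. It is not. The shift exists only if the vaccine works. For a 20% event in 325 subjects randomised 2:1 (about 217 and 108), the standard error is √(0.2 × 0.8 × (1/217 + 1/108)) = 4.7 points against a shift of 1.3. Part A is tabulated separately, so its imbalance does not enter the Part B tables.

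Nor do the documents show that the vaccine already looks more toxic. The March 2014 percentages in Protocol 1.3.1.1 (40 µg, 100 µg, placebo) are 19/23/23 for fatigue and 19/21/26 for injection site erythema. Injection site reaction is higher at 100 µg (8/21/9), but there is no consistent vaccine excess. How much of this precedes placebo removal is not stated, so it does not test the mechanism either way.

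It is also fair that crude TEAE percentages are conventional, that no Part A adverse-event test is specifically planned, that injection counts by group would reveal the imbalance, and that the table mock-ups and the document on adverse events of special interest are separate. The absence of an exposure adjustment can therefore be stated only of the SAP text. None of this removes the problem: side-by-side percentages mislead without a test, and the Week 10 limit is missing from the section that governs the tables.

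**Conclusion.** The point holds for the final cumulative Part A TEAE tables and is limited to them. Early closure of the placebo window, a TEAE window tied to each subject's last dose, and the lack of a common cut are all in the documents. The direction is against both vaccine doses.

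The size is conditional: a crude ratio of about 1.1 to 2.8 with no true difference, or 33% against 21% in the central example. It rests on an assumed removal time and a constant hazard. Reactions concentrated in the first doses would be biased less, and later removal shrinks the effect. The loss of placebo blinding after the Part A analysis adds a reporting effect that cannot be quantified from the documents. Dose selection is unaffected and the Part B effect is minor.

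**What to change.** In SAP 6.11.1:

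1. For Part A between-arm tables, count TEAEs in all three arms only up to the Part A unblinding date, or to Week 10 in line with Protocol 3.5.1.
2. Show later TEAEs of the two active arms in a separate table without a placebo column, with a note that placebo blinding had ended.
3. Add subject-years at risk and first events per 100 subject-years by arm beside the crude percentages.

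The common cut should lead. Rates per subject-year remove the artefact only if the hazard is roughly constant. For early reactions, longer follow-up dilutes the rate in the active arms.

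The same columns in Part B are optional and cheap. The cost is SAP wording and a few extra tables or columns, using dates already collected. No procedure or efficacy analysis changes.
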